We, therefore, plan to examine the association of disadvantaged children's neurobehavioral development i.e., communication, motor skills, problem-solving, and personal-social skills and mother's cognitive function.

Hypothesis: Mothers with better cognitive function will have children with better neurobehavioral development.

Objectives: The specific objectives of the study are (a) to measure the maternal cognitive function, (b) to assess the neurobehavioral development of children.

Methods

Participants

A total of 200 mother-child dyads will participate in the study. Data will be collected by the researcher. Age range of children will range from 12-42 months residing in the slum area located in the city of Dhaka.

Inclusion criteria

Age: 12-42 months on enrolment

Sex: both male and female

Nutritional status: weight-for-age z score (WAZ)>-3SD

Consent: written consent provided by parents

Exclusion criteria

Any child with –

Developmental anomalies,

Known chronic illnesses like epilepsy, tuberculosis,

Twins and multiple births,

Parents not consenting

Sample Size Calculation

Sample size is calculated assuming 5% level of significance, 80% power, an improvement of 0.30 SD neurocognitive developmental scores of children between high and low scorer mother's group, and 15% drop outs, based on the formula below:

$$n = \frac{2(sd)^2}{(M_1 - M_2)^2} \times f(\alpha\beta)$$

Where,

n = sample size per group,

sd=Standard deviation of population=1,

M₁-M₂=Difference between the groups assumed=0.30 SD,

αβ=80% power and 5% significance=8

We need to enroll 150 mother-child dyad.

Measurements

The following measurements will be applied upon all enrolled children's mother:

Bayley Scales of Infant and Toddler Development (BSID-III): Neurobehavioral development of children will be assessed on the revised version of questionnaires of BSID-III. It will be used to assess cognitive, language and motor development of the children. The test has been used in many developing countries, and has been the instrument of choice for child development and nutrition research at this age in other countries like Indonesia and Brazil. It usually takes about an hour to test the children.

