Data Analysis

Participants' responses will be scored according to the scoring systems of the ASQ, BAMSE, and other measures. Data will then be fed to a personal computer and analyzed using the SPSS, version 20. Transformations will be used to normalize the variables when necessary. Data will be analyzed in multiple regression analysis in order to see the relationship between maternal cognitive ability and different domain of child development.

Expected Result and Impact

It is expected that the impact of maternal cognitive function on neurobehavioral development will be considerable.

Although there are few national data for mother's cognitive ability and child's development in Bangladesh, but it can be said that many disadvantaged children are exposed to various

risks for poor development including poverty, malnutrition, poor health and un-stimulating home environment or lack of learning opportunities. Due to poor development, children do poorly in school and subsequently transfer poverty to the next generation. The second UN Millennium goal is to ensure that all children complete primary schooling. The result will help policymakers to take appropriate intervention programs to improve early child development, which, in turn, will achieve satisfactory educational performance. To reach the MDG and to stop the intergenerational transmission of poverty the findings of proposed study will play an important role.

Currently, there are no accepted indicators for child development in Bangladesh. The expected result will help develop country's indicators for child development. Furthermore, the result will provide information to help the setting programs and policies for early childhood development to benefit the disadvantaged children and reduce the persistent inequalities in child development. The proper child development will help make economical and social development of the country.

Time Line

The time plan of the study is described as under

Works	Year								
	1			2			3		
	Quarters			Quarters			Quarters		
	1	2	3	1	2	3	1	2	3
Preparatory works (Manual, SOP, questionnaire preparation)	x								
Site selection	x								
Training		x							
Screening of 1-3.5yr old children & enrolment		x							
Assessment	x	x							
Data entry, cleaning & preliminary analysis			x						
Start writing introduction & method section				x					
Synthesize results & thesis writing					x				
First draft of the PhD thesis						x			
First Seminar							x		

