COVER PAGE

Official Title of the Study : Maternal Cognitive Function and Neurobehavioral Development of Underprivileged Children

NCT Number : NCT03321591

Date of the Document : 19/09/2016

Statistical Analysis Plan: Data will be analyzed by using correlation and multiple regression analysis in order to see the relationship between maternal cognitive function and neurobehavioral development of children. Furthermore, I have a plan to use path analysis (structural equation modeling). In this regard, I have prepared a model to test as under. It is very tough and time consuming to test model fit equation. I have to study more and more on the books of statistics and experts to handle LISREL or SPSS AMOS software.

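### Does the plan need a stated rule for reading three or four domain regressions against its one directional hypothesis?

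*Protocol*

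**What the plan says.** The Protocol has one hypothesis: "Hypothesis: Mothers with better cognitive function will have children with better neurobehavioral development". Its Sample Size Calculation attaches the only error rate and power to one comparison: "Sample size is calculated assuming 5% level of significance, 80% power", with "an improvement of 0.30 SD neurocognitive developmental scores of children between high and low scorer" mothers as the effect. No domain is named there.

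The aim, just above the hypothesis, spells out the outcome as "communication, motor skills, problem-solving, and personal-social skills", which is four domains. The Measurements section says of the BSID-III: "It will be used to assess cognitive, language and motor development of the children", which is three. Data Analysis plans multiple regression by domain: "Data will be analyzed in multiple regression analysis in order to see the relationship between maternal cognitive ability and different domain of child development". Responses are to be "scored according to the scoring systems of the ASQ, BAMSE, and other measures".

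The SAP plans correlation and multiple regression for the "relationship between maternal cognitive function and neurobehavioral development of children", and adds a path analysis. The path diagram to which it refers is not in the available text, so nothing can be inferred from its absence.

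**The concern.** There is one hypothesis, but three or four regressions bear on it, beside a correlation and a path model. If some domains are significant and others are not, the available text does not say whether the hypothesis is supported. The worry is that the reading would be settled after the results are known. Two things would be at stake:

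- **False support.** If any one significant domain in the expected direction counted, the chance of false support would exceed the 2.5% of a single two-sided 5% test read in that direction.
- **Power.** The stated 80% belongs to one comparison and is tied to no rule across domains.

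The Protocol and SAP, dated the same day, also describe the regression outcome differently: by domain in one, as neurobehavioral development in the other. That could suggest disagreement over whether there is one outcome or several.

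**Working it through.** **1. The plan's own figure.** The sample-size formula with SD 1, difference 0.30 and multiplier 8 gives 2 × 1 / 0.09 × 8 = 177.8, so 178 per group and 356 in total. With 15% dropout the total is 355.6 / 0.85 = 418.3, so 419. The stated 150 is not reproduced, and the Participants section says 200. That is a separate matter. Only the 0.30 SD effect and the two enrolment figures are used below.

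**2. Effect on a continuous scale (assumption: median split of a normal maternal score).** The halves of a standard normal score differ by 1.596 SD on average, so r = 0.30 / 1.596 = 0.188.

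**3. Power for one domain.** The mean of z is atanh(0.188) × √(N − 3), with atanh(0.188) = 0.190.
- N = 200: mean 2.67, power Φ(2.67 − 1.96) = 76%.
- N = 170 (200 less 15%): mean 2.46, power 69%.
- N = 150: mean 2.31, power 64%.

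**4. Two extreme rules, three domains.** Equicorrelated normal z values share the mean in step 3, and a domain is positive if z > 1.96. The inter-domain correlation is not in the documents and is varied over 0.5 / 0.7 / 0.9. No covariates are used.

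| N analysed | Any one positive | All three positive | Rules disagree |
|---|---|---|---|
| 200 | 93 / 90 / 84% | 55 / 61 / 68% | 38 / 29 / 17% |
| 170 | 89 / 85 / 78% | 46 / 52 / 59% | 44 / 33 / 19% |
| 150 | 86 / 81 / 74% | 39 / 45 / 53% | 47 / 36 / 20% |

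With four domains at N = 200 the disagreement is 46 / 35 / 20%. These are illustrations, not bounds. A correlation of 0.3 gives 45% for three domains at 200. A Bonferroni-adjusted any-domain rule reduces the 38–17% to 30–8%.

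**5. No true effect.** Support in the expected direction occurs in 6.3 / 5.5 / 4.2% of studies if any one of three domains suffices. If the domains were independent it would be 1 − 0.975³ = 7.3%. If all three are required it is 0.2 / 0.4 / 1.1%. Inflation above 2.5% therefore needs the any-one rule, which the plan does not state.

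**6. What a prespecified decider would buy or cost.** Take the mean of three standardised domain scores.
- Shared effect: its correlation with the maternal score is 3r / √(3 + 6ρ) = 0.230 / 0.210 / 0.195. Power at 200 is 91 / 85 / 79%, or 2–5 points below the any-one rule.
- Effect in one domain only: the correlation is a third of that, and power at 200 is 19 / 17 / 15%, against about 76% for the any-one rule and 61% with Holm adjustment.
- Shared effect with Holm: 84 / 79 / 71% at 200, which is 9–13 points below the any-one rule.

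No option is best under both patterns of effect.

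**7. Do the two documents conflict on the outcome?** The aim defines neurobehavioral development by listing its domains, and the Introduction speaks of different domains of that outcome. Read with these, the SAP phrase is shorthand for the same domains that Data Analysis names. The documents agree.

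**The case for a change.** The strongest case for a change is that this is not a purely descriptive study. It states a directional hypothesis with a significance level and a power, and it expects the result to inform policy. A reader will want to know whether the hypothesis was supported, and in a sizeable share of studies the answer depends on a rule fixed only afterwards. A few SAP sentences would settle that, with no new data.

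Part of this stands. The available text gives no rule, the arithmetic is right, and changing the assumptions mostly raises the disagreement. The mismatch between the BSID-III under Measurements and the ASQ under Data Acquisition and Data Analysis is also real. It concerns which instrument supplies the domains, not how their results are combined, and it is a separate question.

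The rest is weaker. The two rules compared are the extremes of what could be imagined, and neither is attributed to the plan. The study is an observational survey whose listed objectives are to measure maternal cognition and assess child development, and its analysis is framed as describing a relationship. A mixed pattern across domains is then a finding to report, not a trial decision that must come out yes or no. The unnamed covariates are likewise missing detail, and the path diagram may show some of them.

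**Conclusion.** No change follows. The gap is one of unstated detail: the plan gives no rule for combining domains, and no rule that it does give is shown to lead to a wrong result. The domain regressions remain valid estimates of what the Protocol says it will examine. An analyst would sensibly report every domain coefficient with its confidence interval, and describe support as general or confined to particular domains.

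The 17–38% disagreement at 200 (19–44% at 170, 20–47% at 150) rests on a median-split conversion to r = 0.188, an effect shared by three domains, unadjusted two-sided 5% tests, no covariates and an assumed inter-domain correlation of 0.5 to 0.9. It measures the distance between two readings that the plan does not contain.

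Imposing one deciding analysis would be a fair trade-off, not a correction. A composite costs 2–5 points of power at 200 for a shared effect, but falls to 15–19% against about 76% if the effect lies in one domain. The apparent conflict between the SAP and the Data Analysis section disappears once the Protocol's own definition of the outcome is applied.

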COVER PAGE

Official Title of the Study : Maternal Cognitive Function and Neurobehavioral Development of Underprivileged Children

NCT Number : NCT03321591

Date of the Document : 19/09/2016

Statistical Analysis Plan: Data will be analyzed by using correlation and multiple regression analysis in order to see the relationship between maternal cognitive function and neurobehavioral development of children. Furthermore, I have a plan to use path analysis (structural equation modeling). In this regard, I have prepared a model to test as under. It is very tough and time consuming to test model fit equation. I have to study more and more on the books of statistics and experts to handle LISREL or SPSS AMOS software.

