of poor development because they represent different types of biological and psychosocial risks. Poverty is related to inadequate food, and poor sanitation and hygiene that increase infections and stunting in children. Poverty is also connected to poor maternal education, increased maternal stress and depression (Bradley & Corwyn, 2002; Hamadini & Grantham-McGregor, 2004; Baker-Henningham et al., 2003), and deficient stimulation in the home (Schady & Paxson, 2005). All these factors deleteriously affect child development which, in turn, produces poor school achievement, which is further worsened by poor family support (Grantham-McGregor et al., 2007). Risk factors associated with poverty frequently happen together, and degree of development becomes lower with the number of risks factors (Rutter, 1989). Deficits in child development are often occurred in infancy (Feinstein, 2003; Espy et al., 2001) and increase further with age (Richter et al., 1998; Walker & Grantham-McGregor, 1990; Lozoff & Teal, 2004). Several longitudinal studies have found substantial association between socioeconomic status and parental wealth at birth, and cognitive attainment (Sigman et al., 1991; Stein et al., 2005). Poverty and sociocultural background increase children's exposure to psychosocial risks that influence development through behavioral changes (Walker et al., 2007).

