Parenting factors like cognitive stimulation or learning opportunities facilitates early cognitive development. Several studies examined the effect of stimulation or intervention on children from developing countries, including children living in poverty, which strongly supports the importance of early cognitive intervention for facilitating better cognitive and non-cognitive outcomes (Grantham-McGregor et al., 1991; Gardner et al., 2003; Eickmann et al., 2003; Kagitcibasi et al., 2001; Magwaza, 1991). Research revealed three aspects of parenting associated to young children's cognitive and social-emotional competence: cognitive stimulation, caregiver sensitivity and responsiveness to the child, and caregiver affect (National Research Council and Institute of Medicine, 2000). Regarding maternal sensitivity and responsivity several researches reported that these factors are associated with more secure infant attachment (Posada et al., 1999; Eomlinson et al., 2005) and higher cognitive ability (Agarwal et al., 1992) respectively. Appropriate caregiver-child interactions facilitate early social-emotional development and learning materials promote age-appropriate language and problem-solving skills (Walker et al., 2007). Furthermore, maternal depression is another risk factor that causes reduced levels of cognitive function and higher levels of behavior problems (Patel et al., 2003). These factors discussed above are the part of maternal cognitive function which implies that there might be a link between factors evolved from maternal cognitive state and child development. Rubalcava and Teruel (2004) showed that maternal cognitive ability works as an important factor in progressing her children's height, even after controlling for child's age and gender, parental age, mother's and father's years of schooling and mother's height.

Iodine deficiency and iron deficiency anemia threatens the development of many children. Recent research highlights the evidence for other risk factors encompassing intrauterine growth restriction, malaria, lead exposure, HIV infection, institutionalization, and exposure to societal violence (Walker et al., 2011). Notably, breastfeeding and higher

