The Bangla Adaptation of Mini-Mental State Examination (BAMSE): The Bangla adaptation of Mini-Mental State Examination (BAMSE) will be used to assess the cognitive function of mothers. BAMSE is the Bangla adaptation of Mini-Mental State Examination (MMSE). MMSE (Folstein et al., 1975) is a commonly used brief global instrument that measures cognitive abilities having orientation to time and place, memory and attention, language

skills, and visuo-spatial abilities. A good association ($r=0.57$) was found between the MMSE and BAMSE instruments (Kabir & Herlitz, 2000). Test-retest reliability of BAMSE was satisfactory ($r=0.70$) and BAMSE was found to be less sensitive to age and education than the MMSE (Kabir & Herlitz, 2000).

Anthropometry: Weights, heights, Mid-upper arm circumference (MUAC), and head circumference of all the study children and their mothers will be measured according to standard techniques (Lohman et al., 1989; WHO, 1983). Afterwards these anthropometric measures will be converted into height-for-age (HAZ), weight-for-height (WHZ), and weight-for-age (WAZ).

Socioeconomic status (SES): Information will be obtained on the families' house-hold possessions, standard of housing, family structure, and parental education and occupation. The indices described will be calculated to measure the socioeconomic status of the family: 1) housing, on the basis of the condition of the roof and walls of the house and presence or absence of electricity in the house; 2) sanitation, according to ratings of type of latrine and availability of water inside or outside the house; 3) assets, based on the possession of certain household items; and 4) crowding, composed of the number of people per room.

Procedures

Data Acquisition

Standard data collection procedures will be followed in the study. The author of this research proposal will conduct a house-to-house survey in the study area. At first, the general purpose of the study will be briefed to the parents. After having written consent from the parents, they will be asked for information about their children's development (extended ASQ), and their cognitive function (BAMSI). Anthropometric measures will be taken both for mothers and their children in order to have Body Matched Index (BMI). After administration of the all questionnaires, mothers will be interviewed to obtain information on socio-demographic characteristics. Thus data collection will be completed approximately in three months.

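### Does listing a correlation beside the multiple regression leave the study's main result unadjusted for poverty and schooling?

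*SAP*

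**What the plan says.** The hypothesis in the protocol is one of association: "Mothers with better cognitive function will have children with better neurobehavioral development". For the analysis, the protocol's Data Analysis section says: "Data will be analyzed in multiple regression analysis in order to see the relationship between maternal cognitive ability and different domain of child development". The SAP, with the same date, says: "Data will be analyzed by using correlation and multiple regression analysis in order to see the relationship between maternal cognitive function and neurobehavioral development". It goes on to announce a path analysis (structural equation model), whose diagram is not in the text available for review.

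Neither document says which analysis is primary, and the readable text lists no regression covariates. The candidates are collected. Under Socioeconomic status the protocol says: "Information will be obtained on the families' house-hold possessions, standard of housing, family structure, and parental education and occupation". It also defines indices of housing, sanitation, assets and crowding. The Anthropometry section has mothers as well as children measured, and Data Acquisition includes a socio-demographic interview.

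**The concern.** The protocol gives its own reasons to expect confounding. The Introduction says "Poverty is also connected to poor maternal education, increased maternal stress and depression" and, of the factors in that paragraph, "All these factors deleteriously affect child development". That describes a common cause of exposure and outcome. The same section cites a study in which maternal cognitive ability was related to child height "even after controlling for child's age and gender, parental age, mother's and father's years of schooling and mother's height". Under Expected Result and Impact the protocol writes: "It is expected that the impact of maternal cognitive function on neurobehavioral development will be considerable".

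A plain correlation takes no account of poverty or schooling. If it stands beside the regression without a ranking, the same data could give two answers to one hypothesis: a significant correlation and a non-significant adjusted coefficient for the mother's score on the Bangla Mini-Mental State adaptation (BAMSE). A reader could then be shown the more favourable one. An unlisted covariate set also leaves room to choose the adjustment after seeing the data.

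**Working it through.** **1. The texts side by side.** Multiple regression is in both documents; correlation is in the SAP only; path analysis is in the SAP only. No sentence makes the correlation the test of the hypothesis. A multiple regression has more than one predictor, and the socioeconomic and education items are the natural ones to enter.

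**2. Inputs for an illustration.** Neither document gives a figure for crude against adjusted results, so there is none to reproduce. From Sample Size Calculation come a difference of 0.30 SD between children of high- and low-scoring mothers, a 5% level and 15% dropout. Enrolment is 150 there and 200 under Participants, a conflict that is a separate matter. The analysed number then runs from 150 × 0.85 = 127.5, taken as 128, up to 200.

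The 0.30 SD becomes a correlation in one of two ways:
- median split of a normal score: r = 0.30 / (2 × 0.798) = 0.188
- point-biserial: r = 0.30 / √(0.30² + 4) = 0.148

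Assumed, because the documents give nothing: one socioeconomic score that correlates a with BAMSE and b with the child's score.

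**3. Formulas.** Adjusted (partial) r = (r − ab) / √((1 − a²)(1 − b²)). If there is no adjusted association, the crude correlation is r = ab. The percentages come from simulating trivariate normal data, 20,000 studies per cell, two-sided 5%. The ranges span 128 to 200 dyads.

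| a / b | Crude r if no adjusted association | Correlation significant in that case | Adjusted r if crude r = 0.188 | Correlation significant, adjusted not (crude r = 0.188) | Same, crude r = 0.148 |
|---|---|---|---|---|---|
| 0.1 / 0.1 | 0.01 | 5% | 0.180 | 4–5% | 5% |
| 0.2 / 0.2 | 0.04 | 7–8% | 0.154 | 16–18% | 15–20% |
| 0.3 / 0.3 | 0.09 | 17–24% | 0.108 | 34–43% | 28–42% |
| 0.5 / 0.4 | 0.20 | 63–81% | −0.015 | 55–75% | 38–54% |

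With no adjusted association, the adjusted test stays at about 5% in every row.

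The last row needs care. With crude r = 0.188 the adjusted r is (0.188 − 0.20) / √(0.75 × 0.84) = −0.012 / 0.794 = −0.015. With crude r = 0.148 it is −0.052 / 0.794 = −0.066. The largest percentages therefore assume a true adjusted association that is already slightly negative.

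**4. What this measures.** The table shows how often two statistics disagree under assumed confounding. It does not show how often the plan gives a wrong answer. That would need the correlation to decide the hypothesis, and step 1 found no text that says so.

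**5. Would a fixed covariate list be a clear gain?** The documents do not settle what should be on it. Maternal education and household conditions may be partly consequences of maternal cognition, so adjusting for them could remove part of a real effect. The cited height study adjusted for mother's height, which this study measures, but the excerpt names no housing or asset indices. The Introduction also puts parenting on the route from mother to child, so the path model may be meant as the main analysis, and its missing diagram may name covariates.

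**The case for a change.** The strongest case for a change is that the protocol describes the confounding, collects the confounders and then assigns none of them to a model. A few sentences in the SAP would settle which estimate stands before results are known, using variables that are almost all planned already (maternal age would have to be confirmed in the interview). The word impact, and the policy use set out under Expected Result and Impact, go further than a bare association.

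The factual part stands: there is no ranking and no visible covariate list, so some freedom of choice remains. Plain correlation is also fairly read as unadjusted.

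The rest carries less weight. The stated aim and hypothesis concern association. The height study is reported as background and sets no adjustment rule for this one. The sentence on impact states an expectation and does not govern interpretation. Reporting simple correlations before a regression is routine and does not displace the regression. Ranking only the correlation and the regression would still leave the path analysis unplaced.

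**Conclusion.** No change to the plan follows. Under assumed confounding, the correlation can be significant without the adjusted coefficient in anything from about 4% to 75% of studies. That range reflects inputs the documents do not give, and its upper end assumes that no positive adjusted association exists. The regression planned in both documents is not affected by the comparison, and the variables for an adjusted estimate are collected. The gap is one of specification: no named primary analysis and no visible covariates. An analyst can fill it sensibly by reading the correlation as descriptive and justifying the adjustment set when reporting.

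This rests on three readings: that the regression will use the socioeconomic and education data collected for the study; that correlation means the simple, unadjusted kind; and that the missing path diagram is a loss in text extraction and not an omission by the investigator.
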